Role ¹	Blinding Status	Tasks (Not exhaustive, may vary by site)
Study Coordinator	Unblinded to participant randomizations as they occur	Eligibility and Selection, Enrollment, Mailing 2 & 3, Consents/Assents, Biospecimen Collection
PI/Clinical Project Director	Unblinded throughout	Oversee study design, resolve implementation issues
Research Assistant	Blinded to Intervention 1 randomization through clinic visit Unblinded to intervention 2	Mailing 1, Pre- and Post-Visit Surveys, Audio Recordings, RoR Parent Mailings, Biospecimen Collection
Data Analyst/Programmer	Unblinded throughout	Generates enrollment reports, ensures clean data
Lab Staff	Blinded to identifying information on participants	Analyzes biospecimens and records results
Genetic Counselor	Blinded to Intervention 1 randomization through clinic visit Unblinded to intervention 2	Post-RoR Provider surveys, Consents/Assents (if necessary)
Clinicians	Blinded to Intervention 1 randomization through clinic visit Unblinded to intervention 2	Post-Visit and Post-RoR Provider Surveys, PhenoTips, Return results

¹ The same person can hold multiple different roles across sites and therefore have different blinding statuses at each.

ENROLLMENT OVERVIEW

This section of the protocol describes the participant enrollment process for NCGENES 2 up to the 1st clinic visit.

Participant Referral

The set of all potential participants in the NCGENES 2 study is comprised of children (less than 16 years of age) referred for a disorder with unknown but suspected genetic etiology, who are scheduled in the Pediatric Neurology or Pediatric Genetics and Metabolism clinics at the University of North Carolina at Chapel Hill, the Pediatric Genetics clinic at East Carolina University in Greenville, NC, or the Pediatric Genetics and Metabolism clinic at Mission Health in Asheville, NC. Each participant will have an initial status of “Referred” in the NCGENES 2 Tracking System. Referred participants’ scheduling and demographic information will either be populated nightly from the UNC Carolina Data Warehouse for Health (CDW)¹ or will be entered manually into the study’s tracking system following review of scheduling information in the Electronic Medical Record (EMR). Study staff will use this tracking system throughout the enrollment and data collection process, starting with manual entry or auto-population of patient scheduling data and the identification of eligible participants.²

Participant Eligibility

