- ¹1 CLIA Molecular Genetics Test Request Form signed/provider-specific² – printed on white paper (See [Appendix XXXIV](#) on page 281)
- 1 BSP Requisition Form printed on blue paper³ (see [Appendix XXXIII](#) on page 279)

Kit assembly before the visit

Place print patient-specific barcode ID labels, both blood tubes, one folded biohazard bag and a folded Molecular Genetics Test Request Form and/or BSP Requisition Form into the second biohazard bag. ALWAYS bring a pair of gloves should you need to handle the blood tubes. A biohazard-labeled cooler bag should also be brought to the clinic appointment for transporting mailing blood tubes to the BSP post-Visit 1.

After the Visit: Collection and Distribution

Each site will follow a slightly different protocol for collecting and distributing blood samples. This section describes the protocol for creating a phlebotomy order, assisting with blood collection, assembling the blood collection kits, and distributing blood samples at each site.

University of North Carolina at Chapel Hill – UNC

Creating EMR Research Phlebotomy Order

Following reveal of randomization #2 to receipt of genomic sequencing and completion of GS consent, but prior to walking the patient to phlebotomy area, the study coordinator will complete an Epic EMR Research Phlebotomy blood draw order ONLY IF a Clinical Phlebotomy order has NOT been initiated by the physician. If clinical draw HAS BEEN ordered, then the research blood collection is piggybacked on the clinical draw. Detailed instructions for creating a blood draw order can be found in [Appendix XXVII](#) on page 263.⁴ EPIC orders require a 3-step process: 1) creation of the order, 2) approval by the ordering physician, and 3) approval by phlebotomist before the phlebotomist draws the blood.

Blood Collection

Once an order has been created, the SC should assist the participant and parent with navigating the process of the blood draw.

¹ **ONLY** for ECU and UNC. Mission creates Molecular Genetic Test Request electronically

² A UNC MGL form will need to be signed by each physician on the study team one time – then these can be photocopied for use throughout the study. The study coordinator will select the appropriate MGL/CLIA lab physician's form to include with the blood kit.

[figure not shown]
³ The BSP Requisition Form is printed on blue paper to easily distinguish which form is which when both are folded and placed in separate blood bags

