The blood tubes for the MGL may be tubed/chuted (using the tubing station in the Phlebotomy area or behind the Pediatric Check-out desk (near the pediatric consult room). One specimen within the biohazard bag that includes the correct MGL request form should be placed in the tube and sent to the Core lab (tube station #30) or delivered to Core Lab by hand (they will deliver it to the MGL).¹

Tubes for research exome sequencing should be delivered to the BSP, located on 3rd floor of Michael J. Hooker Building/Gilling School of Public Health. Study staff delivering specimens to the BSP will need access to this building on their UNC one card. At the BSP, blood samples should be logged in using the LIMS system (for detailed instructions on entering blood samples into the LIMS, see [Appendix XL](#) on page 286)

How is delivery tracked? The NCGENES 2 study coordinator logs that the samples have been delivered to each lab in the Tracking System by completing the “Visit 1 Biospecimen Collection” task (See page 154 [for more info](#)). The entry of the specimens into the BSP LIMS will be the indication that the BSP lab has received the sample. The entry of the specimen into RENCI Genomic Molecular Workbench by the MGL/CLIA lab will indicate that the CLIA lab has received the sample.

East Carolina University – ECU

Creating EMR Research Phlebotomy Order

Following reveal of randomization #2 to receipt of genomic sequencing and completion of GS consent, but prior to walking the patient to phlebotomy area, complete an Epic EMR Research Phlebotomy blood draw order ONLY IF a Clinical Phlebotomy order has NOT been initiated by the physician. If clinical draw HAS BEEN ordered, then the research blood collection is piggy backed onto the clinical draw. Detailed instructions for creating a blood draw order can be found in [Appendix XXVII](#) on page 263.² ECU EPIC orders require a 3-step process: 1) creation of the order, 2) approval by the ordering physician, and 3) approval by the phlebotomist before the phlebotomist draws the blood.

Blood Collection

[figure not shown]
1. Walk patient and parent to main lab in the UNC Women’s Hospital lobby. Get a number from the clinic dispenser.
2. The parent will inform the phlebotomy worker at the check-in desk that their child needs labs. The SC or the parent should notify the worker that one of the labs is for research.
3. Accompany the family to the blood drawing area/station when their number is called.

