25. While parent is doing post-visit survey, consult with the physician regarding developmental age of child (only if 7 years of age or older chronologically) and any planned blood orders. Also identify if any time sensitive blood collections are needed (e.g., those needed by 3pm, etc.). Relay this information to the Study Coordinator in-person or by text.
26. When parent is done with the survey let them know that you will now take them to the Study Coordinator (who they may have spoken with by phone before today's visit) who will talk to them about a potential next test and provide snacks/reimbursement. When the SC is finished seeing the parent they will direct them to the check-out area and then take them to the phlebotomy area if their child needs to have any blood drawn.
27. Collect the iPad and walk patient and parent to consultation room and hand off folder and patient to Study Coordinator⁴
28. Double check to be sure that you have all tablets, iPads and audio recorders that were brought to the clinic
29. Return to the office and place all electronic devices on chargers in preparation for the next clinic

¹ If unable to record the study ID number, then on the intake form, you received from the parent, write the number of the recorder that was placed in the room.

² NEVER unblind the physician or genetic counselor to the randomization status of the patient (either pre-visit prep or genomic sequencing). If this happens a NOTE should be placed in the participant's tracking system record. The physician and genetic counselor can ONLY be unblinded to patient's randomization status AFTER the physician has completed the post-visit 1 physician survey

³ If the Intake form was not entered by the RA during the clinic visit, it should be entered after the Study Coordinator returns with the folder from the clinic or immediately the next morning. Intake forms should be entered within 24 hours of collection.

⁴ To date we have used the UNC consultation room in Pediatrics clinic (behind check out) primarily, but have also used the cardiology conference room

Study Coordinator Pre-Clinic and In-Clinic Activities
(10/7/2019)

Before clinic visit:

- Log into the NCGENES tracking system¹ to review potential study participants
- Once in tracking, select a referred patient scheduled to visit the clinic three or more weeks from the date of review, starting with the closest appointment date
- Log into EPIC and navigate to the selected patient's medical record information.

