12. In the Order Mode box, type “per” and hit enter. Then choose “Per protocol: cosign required” by clicking on that option. NOTE: there are 3 courses (2 in person) for EPIC research training that will allow a staff member to pend research blood order. The research blood draw order (8243) must be set up in EPIC ahead of the appointment so that the physician can sign it. It has to be put in as a “LAB” not as a “CLINIC” order if phlebotomy is drawing the blood which will always be the case. If the patient is randomized to no sequencing or doesn’t show/cancels, the Epic blood order can be cancelled.)

Providers

Ordering Information

Order mode

per

Ordering provider
YOUR NAME HERE

Authorizing Providers

For procedures

Title
Per protocol: cosign required
Per protocol: no cosign required

Cosigners

For procedures

Cosign required

Accept **Cancel**

13. In the Authorizing provider box, begin typing the name of the attending physician that the participant is seeing in a UNC Pediatric Specialty Clinic, and hit Enter. Select the correct physician by clicking on their name. Then click Accept.

Providers

Ordering Information

Order mode

Per protocol: cosign required

Ordering provider
YOUR NAME HERE

Authorizing Providers

For procedures

fan

[figure not shown]
%	ID	Provider	Verified	Title	Provider Type	Specialty	Street Address	Phone
■	3375	[name]	Yes	MD	Physician	Nephrology	[name]	[name]
■	1379	[name]	Yes	MD	Physician	Neurology	[name]	[name]
■	20154...	[name]	Yes	PAC	Physician As...		[name]	[name]
■	11238	[name]	Yes	MD	Physician		[name]	[name]
■	86014	[name]	Yes	MD	Physician		[name]	[name]
■	62198	[name]	Yes	MD	Physician		[name]	[name]

Accept **Cancel**

14. Click on the red text “No cosigner entered.”

15. Search for the same attending physician to co-sign the visit. Select their name, then click the green sign visit box.

WHY DO I NEED TO KNOW THIS?

If you have Research Coordinators (RCs) on your staff who are not licensed providers, they have the ability to “pend” orders in Epic, but cannot sign them. Having RCs pend orders for research patients ahead of time can be a time saver for the provider, but RCs cannot carry out an order until you (the provider) sign off. So, once a RC pends an order, where can you find it so you can sign it?

THE INFORMATION YOU NEED

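### Physicians are to stay blind to the sequencing assignment until their post-visit survey is done, but the roles table and the UNC/ECU blood-order steps leave room for earlier disclosure

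*Protocol*

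**What the plan says.** Appendix IV, footnote 2 of the research assistant's in-clinic list, covers both randomizations: "NEVER unblind the physician or genetic counselor to the randomization status of the patient (either pre-visit prep or genomic sequencing". Its last sentence permits unblinding only "AFTER the physician has completed the post-visit 1 physician survey", and it asks for a note in the tracking record if unblinding happens.

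The table under NCGENES 2 Clinical Study Roles gives clinicians and genetic counselors this status: "Blinded to Intervention 1 randomization through clinic visit Unblinded to intervention 2". The intervention 1 part has an end point. The intervention 2 part has none and does not mention the survey.

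The Biospecimen Protocol (UNC, Creating EMR Research Phlebotomy Order) places the research blood order "Following reveal of randomization #2 to receipt of genomic sequencing and completion of GS consent, but prior to walking the patient to phlebotomy area", and only when the physician has not already ordered a clinical draw. It adds that "EPIC orders require a 3-step process: 1) creation of the order, 2) approval by the ordering physician", with the phlebotomist third. The ECU section uses the same timing and says "ECU EPIC orders require a 3-step process: 1) creation of the order, 2) approval by the ordering physician". Both sections point to Appendix XXVII for instructions, and step 12 there says: "The research blood draw order (8243) must be set up in EPIC ahead of the appointment so that the physician can sign it". The same step allows cancellation if the child is randomized to no sequencing, does not show or cancels.

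**The concern.** Two rules differ on when a clinician may know the sequencing assignment, and two rules differ on when the research blood order is created. The second conflict falls in the interval that the first leaves unclear. An order created only for children already assigned and consented to sequencing tells the approving physician the assignment.

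The Post-Visit 1 Clinician Questionnaire may still be open at that moment. Item 5 asks how likely exome sequencing is to give this child a diagnosis. Item 22 asks whether the physician's recommendations would differ if exome sequencing could be obtained. A physician just asked to approve the study's sequencing draw may answer these differently from one who does not know. At stake are consistent blinding across staff and the clean use of those two items.

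**Working it through.** No sample-size or power figure is involved. The check is to set the texts in time order.

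1. **When the assignment exists.** Under Study Intervention 2 (If the Parent Consents), the assignment is disclosed after the clinic visit, once consent form 1 and the HIPAA form are signed. Footnote 2's sequencing clause can therefore operate only from that reveal until the survey is complete. The roles table is silent on exactly that interval.

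2. **Who is called on after the reveal.** The laboratory request form does not disclose anything child by child, because it "will need to be signed by each physician on the study team one time" and is then photocopied. In the UNC section the Epic order is the only step that calls on the physician after the reveal. The provider guidance in Appendix XXVII says pended orders do not reach the physician's In Basket and that study staff must contact the physician directly. The request is therefore an active contact about a named child.

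3. **Whether the survey must be done by then.** The intended order is survey first:
   - Compiling the Participant Folder puts the clinician survey ahead of the sheet separating research assistant from coordinator forms, and ahead of the consent to randomization 2.
   - The Appendix XLII research assistant checklist leaves a reminder on the physician's computer during the visit.
   - The tracking system numbers the clinician survey task 13 and Randomization to Genome Sequencing task 15.

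   None of these is a gate. Visit 1 Post-visit Physician Survey and PhenoTips lets the physician complete the survey alone, with reminders every 24 hours after the visit.

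4. **The two order timings.** Under the UNC and ECU sections the sequence is visit, reveal, sequencing consent, order, physician approval, draw. Under Appendix XXVII the order precedes the appointment and hence randomization 2, so signing it at that stage discloses nothing. One order cannot follow both.

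5. **Who is affected.** UNC children, and ECU children if ECU works as written, who are assigned and consented to sequencing, have no clinical draw, and whose physician's survey is still open. Mission's order step asks for no physician approval and is outside the point.

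6. **Ceiling.** Planned enrollment is 850 (800 in the overview diagram), randomized 1:1 (Appendix III). Sequencing assignments: 850 × 1/2 = 425, or 800 × 1/2 = 400. Split by intervention 1 arm: 425/2 = 212.5, or 400/2 = 200. Losses before randomization 2, Mission children, children with a clinical draw and surveys already submitted all come off this ceiling. The protocol gives a rate for none of them.

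7. **Cancellations if every order is placed beforehand.** With no losses, the No GS arm alone gives 850 − 425 = 425 of 850, or 50%. No-shows, refusals of consent form 1 or HIPAA, sequencing decliners, withdrawals at Visit 1 and clinical draws that replace the research order all add to this, so the share exceeds half.

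**The case against.** The survey is plainly meant to come before randomization 2, and footnote 2 already foresees early unblinding by asking for a note. The footnote hangs on a step that tells clinic staff the visit can begin, before any sequencing assignment exists. The ECU text is copied from UNC (it sends ECU families to a UNC lobby), so ECU practice is uncertain. The roles table could equally be taken as the governing text and footnote 2 narrowed, since the protocol names no analysis that needs this blind.

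Much of this stands. It shows that the lapse is not the intended course and that its reach is narrow. It does not remove the conflict. Intended order is not a precondition, the order steps do not call for the note, and footnote 2's last sentence is a general rule on when the physician may be unblinded. Which text prevails is for the study team, but one must; keeping the footnote is cheap and protects items 5 and 22.

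A reader might infer that the trial's comparisons are biased. The documents do not support that. The survey describes a visit held before randomization 2, and no sequencing versus no-sequencing comparison of these items is named. Appendix III also intends sequencing to be balanced across the intervention 1 arms, so exposure should be about equal in them. A reader might also infer a breach for every child in the sequencing arm. The route needs all the conditions in step 5 of the working. Nor do the example tracking screen with the clinician survey pending (a No Exome child) or the Mission coordinator checklist, with its late reminder, show the route in use at UNC or ECU.

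**Conclusion.** The point holds as a conflict between written rules with a limited consequence. Footnote 2 and the roles table disagree on the interval from reveal to survey completion, and the UNC and ECU sections disagree with Appendix XXVII on when the order is created. Under the UNC and ECU wording, the blind that footnote 2 promises is not assured for sequencing children without a clinical draw. The subset may be small; its size and any shift in answers are unknown, and the 425 ceiling does not measure it. The conclusion assumes that staff follow the UNC and ECU sections rather than Appendix XXVII, and that ECU works as written.

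The counselor clause is a separate wording conflict. Footnote 2 names the counselor, yet Study Intervention 2 and the Appendix XLII coordinator checklist have the counselor take sequencing consent on the visit day. Counselors do not complete this survey, so its answers are not affected.

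**What to change.** Reconcile the roles table, the UNC and ECU order sections, Appendix IV footnote 2 and Appendix XXVII step 12 to one blinding and order-timing rule, and confirm what ECU does.

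- **Preferred rule.** The clinician survey is submitted before a post-reveal order goes to the physician for approval. Where that would delay the family, proceed and record the note footnote 2 already requires. State this in the order steps.
- **Roles table.** Add footnote 2's time limit to the clinicians' intervention 2 entry.
- **Counselor clause.** Align it with Study Intervention 2 and Appendix XLII.
- **Flag.** Mark surveys completed after randomization 2, so that any use of items 5 and 22 can be repeated without them. The Status Dates tab carries the second randomization. Its example shows dates only, so same-day ordering needs the History tab, whose example entry is timed to the second. First confirm that survey completion is logged there.
- **If the pre-appointment order is kept instead.** A cancellation must not reach the physician before the survey is in, because it too would show the assignment. More than half of such orders would be cancelled.

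The cost is wording in five places plus the counselor clause, one flag from existing records, and a short wait or an added note for some families.
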